Based on available literature and our pilot data (shown below), **we hypothesize that insulin resistance (IR) and decreased cardiac fitness are central to the NAFLD in adolescents, and the degree of steatosis is negatively correlated with lower fitness and higher IR. Thus, exercise-driven improvements in IHTG levels will be positively associated with the increase in fitness and the decrease in IR levels in adolescents with NAFLD.** We will test our hypotheses through the following specific aims:

Aim 1: Assess the change in IHTG, and CVD and IR markers in subjects with NAFLD after 4 weeks of HIIT, compared to a sex-matched control group also with NAFLD with no training.

1A. Quantitate the change in IHTG. Hypothesis: IHTG will decrease after HIIT, and the change will be greater than that seen in controls.

1B. Measure the changes in fitness and markers of CVD. Hypothesis: HIIT will significantly increase fitness, decrease heart rate variability and blood pressure, and improve atherogenic lipid profile. The changes will be greater than that seen in controls. Changes in fitness and IHTG will correlate.

1C. Estimate changes on IR. Hypothesis: HIIT will decrease IR especially in those with higher baseline IR, and the changes will be greater than that seen in controls. Changes in IR will correlate with changes in fitness and IHTG.

Aim 2: Determine the post-intervention effects of HIIT on IHTG, and CVD and IR markers 3 months after completion of the HIIT in adolescents with baseline NAFLD.

2A. Quantitate the change in IHTG percent. Hypothesis: HIIT will have a sustained positive effect on IHTG, and that IHTG 3-months post-HIIT will be significantly lower compared to baseline level.

2B. Estimate changes on IR and other CVD markers. Hypothesis: HIIT will have a sustained positive effect on IR, and that IR 3-months post-HIIT will be significantly lower compared to baseline level.

Pediatric NAFLD has serious cardio-metabolic health outcomes. Findings of this study will inform clinical providers in the use of HIIT as a modality to treat adolescent NAFLD and associated morbidities, and produce preliminary data for mechanistic studies to probe pathways implicated in the pathogenesis of NAFLD.

Preliminary Results

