We propose a 4-week HIIT intervention in adolescents (ages 13 to 18, inclusive) with NAFLD. Up to 150 adolescents at-risk for NAFLD will be recruited to be able identify enough number of subjects with NAFLD (prevalence of NAFLD in our cohort was 40%; see data analysis section below). Our goal is to have 46 subjects with NAFLD to complete the study. Subjects will be randomized to either an exercise group or control group at a 5:1 ratio.

Because the objective of the study is to assess the effect of exercise in hepatic steatosis, we will use a multi-step approach to identify subjects with NAFLD and without disqualifiers (see

[figure not shown]

Figure 2. Study Design. FMD, Flow-Mediated Dilation; DXA, Dual X-Ray Absorptiometry; OGTT, Oral Glucose Tolerance Test; MRI, Magnetic Resonance Imaging; ACNC, Arkansas Children’s Nutrition Center; HIIT, High-Intensity Interval Training. *These assessments will only be completed if Visit 5 takes place at ACNC. Note: Physical Activity (PA) assessment via FitBit will also be conducted throughout the study.

exclusion criteria). When available, electronic medical records will be reviewed to identify potential participants. Eligibility will be assessed using a screening form. Potential participants may be screened over the phone or in person. If determined eligible, potential participants will be invited to attend a study visit. Study visits will take place at the Arkansas Children’s Nutrition Center (ACNC) and/or Arkansas Children’s Hospital. Parents and/or participants will be instructed not to come to the study visit and other assessments if parent and/or participant is ill. The visit/assessments will be rescheduled if that is case to a time when parents and participants are well and asymptomatic. **Figure 2** summarizes the study visit schedule for the exercise and control groups as described in detail below.

Participants will be asked not to eat or drink anything (except water) after 10 pm the night prior to the study visits. Due to fasting, study visits will be scheduled in the morning. Study compensation will be provided via ClinCard and/or gift card(s). Lunch and/or snacks may be offered to participants and/or parents at study visits.

Baseline/Pre-Intervention: All Subjects

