- Anthropometrics & Vital Signs: Body mass and height will be obtained using standardized techniques. In addition, we will also measure waist and hip circumferences using a tape measure. Blood pressure and heart rate will be assessed using standard techniques. If necessary, participants may be provided with a gown. Measures will be taken in duplicate, or triplicate if not within acceptable agreement.
- FibroScan: A FibroScan (FibroScan® 530 Compact, Echosens, Paris, France) will be performed to determine NAFLD status based on Controlled Attenuated Parameter (CAP) score. FibroScan, similar to an ultrasound scan, is a technique to assess liver health. FibroScan is a routinely used clinical tool in most centers to assess liver health. Outcomes of FibroScan are “Controlled Attenuated Parameter (CAP)” and “Transient Elastogram (TE)”. CAP measurement strongly correlates with steatosis, while TE measures the stiffness of the liver as a surrogate marker of fibrosis, as described above. CAP values range from 100 to 400 dB/m, and higher numbers indicate more pronounced steatosis. TE values range from 2.5 kPa to 75 kPa, and higher numbers indicate more pronounced stiffness (fibrosis). Measurement via FibroScan is done when the subject is lying down on his/her back. The test involves a probe being passed over the right upper quadrant of the abdomen to measure the liver fat content and stiffness. The results are then immediately available for review once the scan is complete. No special preparation is required before the FibroScan. We will use the CAP cut-point of 241 dB/m as suggested by Shin et al. to determine baseline steatosis.⁶⁶ A subject with a CAP score of 241 dB/m or greater will be accepted as having steatosis. FibroScan test takes about 20 minutes to complete including the generation and interpretation of the results.

In the rare instance that a valid scan is not feasible, the participant will be accepted as having NAFLD and will be allowed to proceed with the study. If upon initial Magnetic Resonance Imaging (MRI), the participant is found not to have NAFLD, then participation will be discontinued at that time.

Out of the participants whose eligibility is confirmed:

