Samples will be stored in freezers in the Arkansas Children's Nutrition Center and/or Arkansas Children's Research Institute. The freezers are constantly monitored to ensure that the proper temperature is maintained. Samples will be identified using the subject's unique study acronym along with the date of sample collection and type of sample (e.g. EDTA plasma, serum). Remaining samples may be stored indefinitely or until used up for future analyses. If consented, samples may be used in future studies related liver and/or metabolic health. Participants and/or parents may contact the study's principal investigator, if they choose to withdraw consent to use samples and/or information in future research. In this case, a written letter addressed to the principal investigator expressing their desire to withdraw their consent would be required. If the information and/or samples have been shared or if publication of results has occurred, then we may not be able to remove information and/or samples.

Data Analysis

Exploratory data analysis will be conducted prior to formal statistical analysis. We will examine the distributions of all key variables to check for data errors and ensure that modeling assumptions are not violated. Numerical summaries including means, standard deviations, medians and histogram graphical techniques will be used for continuous variables and frequencies will be computed for categorical variables. For both aims, the primary outcome is IHTG level measured by both FibroScan and MRI, and secondary outcomes are fitness level, and various cardiometabolic disease markers (i.e.; insulin, glucose, adiponectin, etc.). The immediate (Aim 1) and sustained (Aim 2) effect of HIIT will be measured by comparing the changes in outcomes between groups using a linear mixed-effect framework with a subject-level random intercept. Changes in the outcomes are defined as difference between follow up visits (5-week and 3-month) versus the baseline. The independent variables will be group (intervention vs control), visit time (baseline, 5-week, 3-month) and their interaction term. This model specification can test the effect of intervention as well as difference between visits, while correctly account for the within-subject correlation due to repeated visits. Post-hoc contrasts of visit time between 5-week and baseline will be used to test the hypotheses under Aim 1, while contrasts between 3-month and 5-week will be used to test the hypotheses under Aim 2.

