As an exploratory aim, diagnostic performance of FibroScan for the NAFLD adolescent will be determined by discriminating NAFLD status defined by FibroScan against that by MRI to calculate sensitivity, specificity, positive and negative predictive values. Additional agreement statistics such as concordance correlation coefficient and Bland-Altman plots will be provided for the continuous measurements of IHTG levels measured by both methods.

In our pilot data, the IHTG levels were 11.5 ± 5.4 percent at baseline for NAFLD subjects (N=23). With a pre-defined clinically significant change of 20% relative decrease from baseline, we expect the NAFLD subjects' fat percent will be decreased to an average of 9.2 ± 5.4 percent after HIIT intervention, which is an equivalent effect size of 0.43. In order to detect this effect size at 80% power, we will need 38 NAFLD participants in the intervention group, therefore 8 NAFLD subjects in the control group. Accounting for a 20% dropout rate and false-negative screening from FibroScan, we propose to enroll 58 subjects with NAFLD. Therefore, we need to screen no less than 150 subjects at-risk for NAFLD at baseline, to be able to identify 58 subjects with NAFLD (NAFLD prevalence was 40% in our pilot study, see preliminary data section above).

Ethical Considerations

This study will be conducted in accordance with all applicable government regulations and the University of Arkansas for Medical Sciences research policies and procedures. This protocol and any amendments will be submitted and approved by the UAMS Institutional Review Board (IRB) to conduct the study.

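### Data Analysis contradicts itself on Aim 1: effects are to be compared between groups, but the named test is a visit-time contrast that, as worded, does not compare arms

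*Combined protocol and SAP*

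**What the plan says.** Under Objective/Specific Aims, hypothesis 1A is "IHTG will decrease after HIIT, and the change will be greater than that seen in controls". Hypotheses 1B and 1C have the same structure: a change after HIIT, then a larger change than in controls, then correlations.

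Data Analysis says the effect of HIIT "will be measured by comparing the changes in outcomes between groups using a linear mixed-effect framework with a subject-level random intercept". It defines change as follow-up minus baseline and lists the terms: "The independent variables will be group (intervention vs control), visit time (baseline, 5-week, 3-month) and their interaction term". It adds: "This model specification can test the effect of intervention as well as difference between visits". The only sentence that assigns a test to Aim 1 then says: "Post-hoc contrasts of visit time between 5-week and baseline will be used to test the hypotheses under Aim 1". It does not say whether that contrast is taken within the exercise arm, averaged over arms, or differenced between arms.

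The primary outcome is IHTG by both FibroScan and MRI. On entry, the FibroScan text under Study Visit 1 says: "A subject with a CAP score of 241 dB/m or greater will be accepted as having steatosis". Allocation (Study Design and Procedures): "Subjects will be randomized to either an exercise group or control group at a 5:1 ratio".

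**The concern.** A contrast of visit time in a group-by-visit model is ordinarily either the change within one arm or the change averaged over arms. Neither removes what happened to the controls. The question in 1A to 1C that needs randomization is whether HIIT changes the outcome more than no training does, and only the difference between arms in their 5-week changes answers it.

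The choice decides what the main claim rests on. A visit contrast absorbs every shift shared by the arms, such as season, diet, being observed, and regression to the mean after selection on a high reading. Because the two contrasts have very different power at 38 versus 8, an analyst who found the interaction non-significant could point to the operative sentence and report the visit contrast as the Aim 1 result.

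**Working it through.** **1. Do the documents show which reading was meant?**
- The between-group sentence and the interaction term point to a comparison of arms.
- The remark on what the model can test lists the intervention effect and the difference between visits as separate things. The next sentence gives Aim 1 to visit time.
- The same sentence tests Aim 2 by 3-month versus 5-week. The 3-month visit is for the exercise group only, so that contrast can only be within HIIT. The parallel wording suggests the same for Aim 1.

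**2. The plan's own sample size.** The inputs are in Data Analysis: "the IHTG levels were 11.5 ± 5.4 percent at baseline for NAFLD subjects (N=23"), expected to fall to 9.2 ± 5.4. No control change is given. Alpha, sidedness and SD of change are not stated; I assume alpha 5%.
- Effect size: (11.5 − 9.2)/5.4 = 2.3/5.4 = 0.426, against 0.43 stated.
- Paired t test, two-sided, SD of change 5.4: n = 46 gives 80.7% power. Split 5:1, 46 × 5/6 = 38.3 and 46/6 = 7.7, or 38 and 8 after rounding.
- With 38 alone, the two-sided paired test has 72.5% power. One-sided, 36 are needed, and 38 give 82.4%.
- Dropout: 46/(1 − 0.20) = 57.5, so 58, as stated.
- Between groups at 5:1, two-sided, SD of change 5.4: control n = (1 + 1/5) × (1.960 + 0.842)² × (5.4/2.3)² = 1.2 × 7.85 × 5.51 = 52, plus 260 in exercise, total 312.

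The stated figures are therefore close only to a before-after calculation.

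**3. Dilution if averaged over arms.** With a true HIIT fall of 2.3 and no control change, the equally weighted visit contrast estimates (2.3 + 0)/2 = 1.15.

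**4. A shift common to both arms, no HIIT effect** (simulation, 38 versus 8, two-sided 5%). Assume a common IHTG fall of 1.0 point; its size is not in the documents.

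| Assumed baseline/5-week correlation | Within HIIT | Averaged, equal weight | Group-by-visit |
|---|---|---|---|
| 0.5 | 20% | 16% | 5% |
| 0.8 | 42% | 31% | 5% |

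**5. Regression to the mean for CAP.** Entry requires CAP of at least 241 dB/m at Visit 1. The next scheduled FibroScan is Visit 4, so selection and baseline share one reading. Assume normal readings, a proportion p = 0.45 above the cut, and reliability r. Then z = 0.126, φ(z) = 0.396 and φ(z)/p = 0.880. The expected fall with no treatment effect is (1 − r) × 0.880 SD.

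| r | Expected fall (SD) | SD of change (SD) | Within-HIIT test (n=38) declares a fall | Between-group test rejects |
|---|---|---|---|---|
| 0.9 | 0.09 | 0.44 | 23% | about 5% |
| 0.8 | 0.18 | 0.61 | 41% | about 5% |
| 0.7 | 0.26 | 0.74 | 57% | about 5% |

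**6. Power of the contrast that answers Aim 1.** SD of change = 5.4 × √(2(1 − ρ)), and standard error = SD of change × √(1/38 + 1/8). The difference is 2.3 with no control change, two-sided 5%, t on 44 degrees of freedom.

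| Assumed ρ | SD of change | Standard error | Power | Completers for 80% at 5:1 |
|---|---|---|---|---|
| 0.5 | 5.40 | 2.10 | 19% | 312 (52 + 260) |
| 0.8 | 3.42 | 1.33 | 40% | 126 (21 + 105) |
| 0.9 | 2.41 | 0.94 | 67% | 66 (11 + 55) |

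Power reaches 80% when the SD of change is about 2.06 or less, that is, ρ of about 0.93 or more.

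**The case against.** The strongest reply is that the plan already commits to a between-group comparison of changes and puts the interaction in the model. The visit sentence may only say which time points enter that comparison. On that reading the test is the right one and the regression-to-the-mean concern disappears. This stands in part: a reader might infer that the plan has no between-group test for Aim 1, and the documents do not support that. What remains is a contradiction within one paragraph, with the more specific sentence naming the wrong contrast.

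Three further points are fair:
- A visit contrast within HIIT does test the first part of 1A, so it has a legitimate use.
- A reader might take post-hoc to mean chosen after seeing the data. Contrasts computed after fitting a model are often called that, and here the visits are named in advance. The label is unhelpful, but the missing group component is the defect.
- The sample size does not settle the intended reading. The two-sided paired calculation gives 46 in total, whereas the plan says 38 are needed in the intervention group, and alpha and sidedness are unstated.

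The CAP rates depend on assumptions. The documents give no CAP SD, repeatability or proportion above 241. Study Population also allows recruitment of people with an earlier high CAP or MRI-confirmed NAFLD, so one truncation at Visit 1 does not describe the whole sample.

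**Conclusion.** The point holds as an internal contradiction with consequences. As worded, the sentence that decides Aim 1 does not compare arms, and following it could give a wrong conclusion about HIIT relative to control. The literal reading is a live one, because the parallel Aim 2 contrast can only be within HIIT and the sample size is argued from a before-after fall.

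A reader might infer that the trial will count regression to the mean as a HIIT effect. The documents support this only conditionally: it follows if the contrast is taken within HIIT or averaged over arms. The false-positive rates of about 23%, 41% and 57% are illustrations for CAP under assumed reliability and an assumed 45% above the cut. For MRI the effect is indirect, because MRI decides entry only when no valid FibroScan is obtained. Its size depends on a CAP–MRI correlation that is not given.

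The stated 80% power does not carry over to the between-group contrast unless the baseline/5-week correlation is about 0.93 or higher, assuming a 2.3-point difference, an SD of 5.4 at each visit and no control change.

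**What to change.** Replace the Aim 1 half of the contrast sentence with a statement on these lines: the hypotheses that change is greater with HIIT than in controls will be tested by the pre-specified group-by-visit contrast, (5-week minus baseline in HIIT) minus (5-week minus baseline in control), two-sided 5%, for each primary measure. Drop the post-hoc label. Keep the within-HIIT visit contrast for the component that the outcome improves after HIIT, and state that it is not evidence of an effect relative to control.

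Restate power for the between-group contrast, giving alpha, sidedness, the assumed SD of change and the assumed control change.

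The text cost is a sentence or two plus the power paragraph. No visit or measurement changes. The real cost is a less favourable power figure: at 38 versus 8, about 19% to 67% over correlations of 0.5 to 0.9. The sponsor would have to justify a high correlation, revisit the sample size, or describe the controlled comparison as imprecise.

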Participants can bring a friend or family member to workout with them if they would like. A separate release will be signed by the friend or family member in order to workout at the ACNC fitness facility.

5-Week/Post-Intervention: All Subjects

Study Visit 3 – This visit may last up to 3 hours and include: measurement of body mass and height, FMD, pregnancy screening (if female), DXA, and fitness test as described above. Participants who are in the control group will complete this visit 5 weeks \pm 1.5 week after study visit 2. Participants will be reimbursed for their time with \$25 at the end of the visit.

Study Visit 4 – This visit may last up to 4 hours and include: measurement of body mass and height, vital signs, OGTT, FibroScan, urine collection, and dietary questionnaire as described above. Participants will be reimbursed for their time with \$50 at the end of the visit.

3-Month Follow-up: Exercise Group Only

Study Visit 5 – Participants from the exercise group will be asked to attend a follow-up visit 3 months \pm 2 week after last HIIT session. This visit may last up to 4 hours and include: measurement of body mass and height, hip and waist circumference, vital signs, pregnancy screening (if female), DXA, FibroScan, FMD, OGTT, urine collection, and dietary questionnaire as described above. FMD, pregnancy screening (if female) and DXA will only be completed in the instance that this visit takes place at ACNC. Participants will be reimbursed for their time with \$50 at the end of the visit.

Magnetic Resonance Imaging (MRI)

In addition to the study procedures described above, all participants will complete a MRI scan before the baseline/pre-intervention fitness test, and another MRI scan before the 5-week/post-intervention OGTT. Furthermore, participants in the exercise group will complete an additional MRI scan before the 3-month follow-up OGTT. The MRI scans will be done at the Arkansas Children's Hospital Radiology Department for the determination of hepatic fat content via magnetic resonance imaging. Each visit for completion of a MRI scan will last up to 1.5 hours. Participants will be reimbursed for their time with \$50 after each visit.

Physical Activity Assessment

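### Aim 2 predicts values below baseline at 3 months, but its assigned test compares 3 months with 5 weeks, and the stated between-group comparison has no control data at 3 months

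*Combined protocol and SAP*

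**What the plan says.** Under Objective/Specific Aims, Aim 2A predicts that "IHTG 3-months post-HIIT will be significantly lower compared to baseline level", and Aim 2B that "IR 3-months post-HIIT will be significantly lower compared to baseline level". Both are statements about change from baseline after training.

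The Data Analysis section describes the analysis in four steps:

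- Purpose: "The immediate (Aim 1) and sustained (Aim 2) effect of HIIT will be measured by comparing the changes in outcomes between groups".
- Definition of change: "Changes in the outcomes are defined as difference between follow up visits (5-week and 3-month) versus the baseline".
- Model: "The independent variables will be group (intervention vs control), visit time (baseline, 5-week, 3-month) and their interaction term", with a random intercept per subject.
- Tests: for Aim 1, the visit contrast of 5 weeks against baseline. For Aim 2, "contrasts between 3-month and 5-week will be used to test the hypotheses under Aim 2".

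In Study Design and Procedures, the last visit is headed "3-Month Follow-up: Exercise Group Only". The MRI subsection likewise gives the third scan to the exercise group alone. Controls finish after the 5-week assessments and are then offered supervised exercise (Physical Activity Assessment subsection).

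**The concern.** There are two separate faults.

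First, the contrast named for Aim 2 is not the one in its hypotheses. The difference between 3 months and 5 weeks describes rebound or further decline after training ends. If the benefit is fully kept, the true contrast is zero and the test should not reject. If it is fully lost, the test tends to reject, in the direction of worsening.

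Second, the section promises a between-group measure of the sustained effect, but no control is assessed at 3 months. That cell of the group-by-visit table is empty.

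IHTG is the primary outcome for both aims. Followed literally, the plan could report a maintained benefit as a null result. Software would drop the 3-month interaction or return a value that depends on the coding, so a within-arm change could be read as a between-group effect. Changing the contrast after the data are seen would be a post hoc change to a primary-outcome analysis.

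**Working it through.** **Inputs from the Data Analysis section.** Baseline IHTG 11.5, SD 5.4; expected value after HIIT 9.2, SD 5.4; 38 exercise and 8 control completers; 80% power; 20% dropout; 58 enrolled.

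**Assumptions, because the documents do not give them.** Two-sided alpha 0.05; equal SD at each visit; within-subject correlation r of 0.5, 0.7 or 0.8. A paired t test stands in for the within-arm model contrast.

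**The plan's own figures.** The effect size is (11.5 − 9.2)/5.4 = 2.3/5.4 = 0.426, stated as 0.43. A one-sided paired t test at 80% power needs 36, close to the stated 38. A two-sided test needs 46, which equals the total 38 + 8. Enrolment is 46/0.8 = 57.5, rounded up to 58, as stated. The present point does not depend on which reading was intended.

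**Rejection probability of each contrast.** The SD of a change is 5.4 × √(2(1 − r)). For a true change δ the noncentrality is (δ/SD of change) × √38, on 37 degrees of freedom. For δ = 2.3:

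| r | SD of change | δ/SD | Noncentrality | Power |
|---|---|---|---|---|
| 0.5 | 5.40 | 0.426 | 2.63 | 72.5% |
| 0.7 | 4.18 | 0.550 | 3.39 | 91.0% |
| 0.8 | 3.42 | 0.673 | 4.15 | 98.1% |

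Applied to three courses of mean IHTG (baseline, 5 weeks, 3 months), the probability of a significant result is:

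| Course | Contrast | r = 0.5 | r = 0.7 | r = 0.8 |
|---|---|---|---|---|
| Fully kept (11.5, 9.2, 9.2) | 3-month v 5-week (planned) | 5% | 5% | 5% |
| | 3-month v baseline (Aim 2) | 72.5% | 91% | 98% |
| Fully lost (11.5, 9.2, 11.5) | 3-month v 5-week (planned) | 72.5% | 91% | 98% |
| | 3-month v baseline (Aim 2) | 5% | 5% | 5% |
| Half lost (11.5, 9.2, 10.35) | 3-month v 5-week (planned) | 25% | 38% | 52% |
| | 3-month v baseline (Aim 2) | 25% | 38% | 52% |

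The 5% entries are the assumed alpha, because the true contrast is zero. In the fully lost case, half of that 5% (2.5%) would be a significant fall from baseline.

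The planned contrast can confirm a fall only if IHTG keeps dropping after training ends, which Aim 2 does not require. With a 3-month mean of 8.05 and r = 0.5, it is significant in 25% of trials, against 97% for 3-month versus baseline.

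**Estimability.** The fixed effects are an intercept, group, two visit terms (β5 for 5 weeks, β3 for 3 months) and two interactions (γ5, γ3): 6 parameters. Five cells are observed: exercise at three visits and control at two. Every 3-month record belongs to the exercise group, so the columns for β3 and γ3 are identical in the data. The rank is 5, and only the sum β3 + γ3 is identified.

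| Quantity | Expression | Estimable |
|---|---|---|
| Between-group change, 5-week − baseline (Aim 1) | γ5 | yes |
| Within-exercise, 3-month − baseline | β3 + γ3 | yes |
| Within-exercise, 3-month − 5-week | (β3 + γ3) − (β5 + γ5) | yes |
| Between-group change, 3-month − baseline | γ3 | no |
| Between-group change, 3-month − 5-week | γ3 − γ5 | no |
| Visit contrast 3-month − 5-week, averaged over groups | (β3 + γ3/2) − (β5 + γ5/2) | no |

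A random intercept does not fill an empty fixed-effect cell. The last row matters because the plan calls its tests contrasts of visit time. Taken as an average over both groups, the planned Aim 2 contrast cannot be computed at all.

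**The case against.** The strongest reply is that the plan already contains the right quantity. It defines change at both follow-ups against baseline, and 3-month minus baseline within the exercise group is estimable from the specified model. On this view the fault is one inconsistent sentence. That much is true, but the inconsistent sentence is the one that assigns the test, and the definition of change makes the contradiction plainer.

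A second reply is that Aims 2A and 2B also speak of a sustained effect, on which 3-month versus 5-week does bear. This stands in part: the contrast is informative as a secondary estimate, and a significant rise would properly be read as loss of benefit. It cannot carry the hypothesis. Non-significance does not show persistence without an equivalence margin, and the plan gives none. With half the benefit lost, the planned contrast is non-significant in 75% of trials at r = 0.5, 62% at r = 0.7 and 48% at r = 0.8. So it usually misses partial loss at low to moderate correlation, but not at high correlation.

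Third, the between-group wording is one sentence covering both aims, and Aims 2A and 2B do not themselves promise a comparison with controls. This limits the second fault: it concerns the stated comparison at 3 months, not the feasibility of Aim 2. Aim 1 and the sample-size calculation are unaffected.

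**Conclusion.** Both parts hold. The Aim 2 contrast does not test the Aim 2 hypotheses. If the benefit is fully kept, it is significant in 5% of trials, where the hypothesised contrast is significant in 72.5% to 98% for r from 0.5 to 0.8. If the benefit is fully lost, the two sets of figures change places. The sizes depend on the assumed correlation, alpha and sidedness; the inversion does not. Separately, no between-group effect at 3 months can be estimated, whatever the sample size, because one of the six group-by-visit cells has no data. This should be corrected before analysis, because a rule that is written down gives the wrong answer.

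**What to change.** In the Data Analysis section:

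1. Name 3-month minus baseline within the exercise group as the Aim 2 test, for IHTG and for insulin resistance.
2. Keep 3-month minus 5-week within the exercise group as a secondary estimate of rebound, reported with its confidence interval. Do not read non-significance as persistence.
3. Remove the between-group wording for Aim 2, and state that the result is an uncontrolled change within one arm, open to regression to the mean and time trends.
4. Fit the group-by-visit interaction only for baseline and 5 weeks, the visits both arms attend.

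The cost is wording and contrast code, with no new visits, participants or measurements. The price in interpretation is that Aim 2 becomes openly uncontrolled. A controlled 3-month estimate would need control assessments at that time, and the exercise offered to controls after they finish would have to be reconciled with them.
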